6.6.1. Hemorrhage

Bleeding events have occurred in subjects with relapsed/refractory chronic lymphocytic leukemia (CLL) and relapsed/refractory non-Hodgkin's lymphoma (NHL) who received tirabrutinib as monotherapy. These include minor hemorrhagic events such as contusion, hematoma, and petechiae, and major hemorrhagic events such as small intestinal hemorrhage and subdural hematoma.

Consider interrupting treatment with tirabrutinib for up to 7 days prior to surgery or other interventions associated with a significant risk of bleeding and resuming treatment once hemostasis is achieved.

Subjects should be monitored for signs of bleeding and treated appropriately.

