7.1.7. Adverse Events of Interest

The treatment-emergent AEs of interest (AEI) include:

AEI	Grouped Terms
Hemorrhage/Bleeding	MST-CT Bleeding/Haemorrhage (Appendix 4)
Infections	SOC: Infections and infestations
Hypersensitivity	MST-CT Hypersensitivity (Appendix 5)
Cytopenia	MST: Anemia-related events, leukopenias, neutropenia, thrombocytopenias (Appendix 6)
Cardiac Arrhythmias	MST-CT Cardiac arrhythmia and bradycardia_narrow (Appendix 7)
Diarrhoea	PT: Diarrhoea
Rash	MST-CT Rash - specific to ONC (Appendix 8)

The following summaries will be provided for AEs by SOC, PT, and maximum severity:

- A) TEAE
- B) TEAEs leading to dose modifications or temporary interruption of study drug
- C) TEAEs leading to discontinuation of study drug

A data listing of AEs will be provided by alphabetic ascending order of AE name, then by subject ID.

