Appendix 4. Bleeding/Haemorrhage Medical Search Term

Note: The list presented below is based on MedDRA Version 22.0. The actual list will be up-versioned to the MedDRA version used at the time of database finalization.

MEDDRA Preferred Term	PT Code
Abdominal wall haematoma	10067383
Haemorrhagic adrenal infarction	10079902
Eye haematoma	10079891
Spontaneous hyphaema	10080110
Anal fissure haemorrhage	10079765
Paranasal sinus haemorrhage	10080108
Peripheral artery aneurysm rupture	10079908
Aortic annulus rupture	10079586
Peripheral artery haematoma	10081077
Subgaleal haemorrhage	10080900
Von Willebrand's factor antibody	10080829
Nephritis haemorrhagic	10029132
Renal cyst haemorrhage	10059846
Renal haematoma	10038459
Renal haemorrhage	10038460
Ureteric haemorrhage	10065743
Extracerebral cerebral haematoma	10080347
Gastrointestinal vascular malformation haemorrhagic	10080561
Abdominal wall haemorrhage	10067788
Abnormal clotting factor	10049862
Abnormal withdrawal bleeding	10069195
Acquired dysfibrinogenaemia	10051122
Acquired haemophilia	10053745
Acquired haemophilia with anti FVIII, XI, or XIII	10056496
Acquired protein S deficiency	10068370
Acquired Von Willebrand's disease	10069495
Activated partial thromboplastin time abnormal	10000631
Activated partial thromboplastin time prolonged	10000636

MEDDRA Preferred Term	PT Code
Activated partial thromboplastin time ratio abnormal	10075284
Activated partial thromboplastin time ratio fluctuation	10075286
Activated partial thromboplastin time ratio increased	10075287
Acute haemorrhagic leukoencephalitis	10058994
Acute haemorrhagic ulcerative colitis	10075634
Administration site bruise	10075094
Administration site haematoma	10075100
Administration site haemorrhage	10075101
Adrenal haematoma	10059194
Adrenal haemorrhage	10001361
Anal haemorrhage	10049555
Anal ulcer haemorrhage	10063896
Anastomotic haemorrhage	10056346
Anastomotic ulcer haemorrhage	10002244
Aneurysm ruptured	10048380
Angina bullosa haemorrhagica	10064223
Anorectal varices haemorrhage	10068925
Anti factor IX antibody positive	10058748
Anti factor V antibody positive	10058745
Anti factor VII antibody positive	10058746
Anti factor VIII antibody positive	10049013
Anti factor X activity abnormal	10077670
Anti factor X activity increased	10077671
Anti factor X antibody positive	10058747
Anti factor XI antibody positive	10058749
Anti factor XII antibody positive	10058750
Antithrombin III increased	10051115
Aortic aneurysm rupture	10002886

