Cerebral haemorrhage foetal	10050157
Cerebral haemorrhage neonatal	10008112
Cerebral microhaemorrhage	10067277
Cervix haematoma uterine	10050020
Cervix haemorrhage uterine	10050022
Chest wall haematoma	10076597
Choroidal haematoma	10068642
Choroidal haemorrhage	10008786
Chronic gastrointestinal bleeding	10050399
Chronic pigmented purpura	10072726
Ciliary body haemorrhage	10057417
Circulating anticoagulant	10053627
Clot retraction abnormal	10009669
Clot retraction time prolonged	10009675
Coagulation disorder neonatal	10009732
Coagulation factor decreased	10009736
Coagulation factor deficiency	10067787
Coagulation factor IX level abnormal	10061770
Coagulation factor IX level decreased	10009746
Coagulation factor mutation	10065442
Coagulation factor V level abnormal	10061771
Coagulation factor V level decreased	10009754
Coagulation factor VII level abnormal	10061772
Coagulation factor VII level decreased	10009761
Coagulation factor VIII level abnormal	10061773
Coagulation factor VIII level decreased	10009768
Coagulation factor X level abnormal	10061774
Coagulation factor X level decreased	10009775
Coagulation factor XI level abnormal	10061775
Coagulation factor XI level decreased	10009779
Coagulation factor XII level abnormal	10061776
Coagulation factor XII level decreased	10009783
Coagulation factor XIII level abnormal	10061777
Coagulation factor XIII level decreased	10009787
Coagulation time abnormal	10009791

MEDDRA Preferred Term	PT Code
Coagulation time prolonged	10009799
Coagulopathy	10009802
Coital bleeding	10065019
Colonic haematoma	10009996
Congenital coagulopathy	10063563
Congenital dysfibrinogenaemia	10051123
Conjunctival haemorrhage	10010719
Contusion	10050584
Corneal bleeding	10051558
Cullen's sign	10059029
Cystitis haemorrhagic	10011793
Deep dissecting haematoma	10074718
Diarrhoea haemorrhagic	10012741
Dilutional coagulopathy	10060906
Disseminated intravascular coagulation	10013442
Diverticulitis intestinal haemorrhagic	10013541
Diverticulum intestinal haemorrhagic	10013560
Duodenal ulcer haemorrhage	10013839
Duodenitis haemorrhagic	10013865
Dysfunctional uterine bleeding	10013908
Ear haemorrhage	10014009
Ecchymosis	10014080
Encephalitis haemorrhagic	10014589
Endometriosis	10014778
Enterocolitis haemorrhagic	10014896
Epidural haemorrhage	10073681
Epistaxis	10015090
Ethanol gelation test positive	10062650
Exsanguination	10015719
Extra-axial haemorrhage	10078254
Extradural haematoma	10015769
Extravasation blood	10015867
Eye contusion	10073354

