Haemorrhage subepidermal	10019001
Haemorrhage urinary tract	10055847
Blood loss anaemia	10082297
Haemorrhagic arteriovenous malformation	10064595
Haemorrhagic ascites	10059766
Haemorrhagic breast cyst	10077443
Haemorrhagic cerebral infarction	10019005
Haemorrhagic cyst	10059189
Haemorrhagic diathesis	10062713
Haemorrhagic disease of newborn	10019008
Haemorrhagic disorder	10019009
Haemorrhagic erosive gastritis	10067786
Haemorrhagic hepatic cyst	10067796
Haemorrhagic infarction	10019013
Haemorrhagic necrotic pancreatitis	10076058
Haemorrhagic ovarian cyst	10060781
Haemorrhagic pneumonia	10077933
Haemorrhagic stroke	10019016
Haemorrhagic thyroid cyst	10072256
Haemorrhagic transformation stroke	10055677
Haemorrhagic tumour necrosis	10054096
Haemorrhagic urticaria	10059499
Haemorrhagic varicella syndrome	10078873
Haemorrhagic vasculitis	10071252
Haemorrhoidal haemorrhage	10054787
Haemostasis	10067439
Haemothorax	10019027
Henoch-Schonlein purpura	10019617
Hepatic haemangioma rupture	10054885
Hepatic haematoma	10019676
Hepatic haemorrhage	10019677

MEDDRA Preferred Term	PT Code
Hereditary haemorrhagic telangiectasia	10019883
Hermansky-Pudlak syndrome	10071775
Hyperfibrinolysis	10074737
Hypohaema	10020923
Hypocoagulable state	10020973
Hypofibrinogenaemia	10051125
Hypoprothrombinaemia	10021085
Hypothrombinaemia	10058517
Hypothromboplastinaemia	10058518
Iliac artery perforation	10075731
Iliac artery rupture	10072789
Iliac vein perforation	10075744
Immune thrombocytopenic purpura	10074667
Implant site bruising	10063850
Implant site haematoma	10063780
Implant site haemorrhage	10053995
Incision site haematoma	10059241
Incision site haemorrhage	10051100
Increased tendency to bruise	10021688
Induced abortion haemorrhage	10052844
Inferior vena cava perforation	10075742
Infusion site bruising	10059203
Infusion site haematoma	10065463
Infusion site haemorrhage	10065464
Injection site bruising	10022052
Injection site haematoma	10022066
Injection site haemorrhage	10022067
Instillation site bruise	10073630
Instillation site haematoma	10073609
Instillation site haemorrhage	10073610
Internal haemorrhage	10075192
International normalised ratio abnormal	10022592
International normalised ratio increased	10022595
Intestinal haematoma	10069829
Intestinal haemorrhage	10059175

MEDDRA Preferred Term	PT Code
Intestinal varices haemorrhage	10078058
Intra-abdominal haematoma	10056457
Intra-abdominal haemorrhage	10061249
Intracerebral haematoma evacuation	10062025

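### The Hemorrhage/Bleeding adverse event of interest also collects coagulation-test, factor-level and antibody terms and some non-bleeding diagnoses, and no haemorrhage-only count is planned

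*SAP*

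**What the plan says.** SAP Section 7.1.7 defines the Hemorrhage/Bleeding AE of interest by a search list, "MST-CT Bleeding/Haemorrhage", set out in Appendix 4. It does not require that a bleed occurred, and it plans no narrower version. In the same table, the arrhythmia group uses a list labelled narrow.

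Most of Appendix 4 consists of bleeds. It also contains test results and factor levels, for example "Activated partial thromboplastin time prolonged", "International normalised ratio increased" and "Coagulation factor VIII level decreased", and diagnoses such as coagulopathy, inherited factor deficiencies and endometriosis. "Immune thrombocytopenic purpura" appears there and again in Appendix 5 (hypersensitivity). It does not appear in Appendix 6, although Section 7.1.7 describes the cytopenia group as including thrombocytopenias.

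Three summaries are planned for each AE of interest, by system organ class, preferred term and maximum severity: (A) treatment-emergent AEs, (B) those leading to dose modification or temporary interruption, and (C) those leading to discontinuation. A listing by AE name is also planned.

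Protocol Section 6.6.1 describes the bleeding seen with tirabrutinib by examples that are all bleeds: "These include minor hemorrhagic events such as contusion, hematoma, and petechiae, and major hemorrhagic events".

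**The concern.** A reader of a row labelled Hemorrhage/Bleeding will take it as the number of subjects who bled. Under Appendix 4, a subject whose only event is a reported clotting-test abnormality belongs to that group. The same holds for summaries B and C. Protocol Section 7.1.3 makes a laboratory abnormality an AE when it needs intervention or leads to a change in study drug, so the test-only events that do reach the database may well be ones with a treatment action.

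Immune thrombocytopenic purpura raises the reverse problem. An event coded to that term would appear under bleeding and under hypersensitivity, but would be missing from the cytopenia group.

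At stake is the accuracy of one descriptive safety category. No endpoint, comparison or stopping rule uses it.

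**Working it through.** The SAP states no count of these terms, so there is no plan figure to reproduce. The check is a direct count, followed by a comparison of the rules that decide which results can enter.

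**1. Terms in Appendix 4 that name a test, level or antibody**

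| Type | Terms |
|---|---|
| Clotting-time and clot-function tests | 21 |
| Factor, fibrin or fibrinogen, fibrinolysis and related levels | 50 |
| Inhibitor and antibody tests | 10 |
| Sum | 81 |

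- Without the two bleeding-time terms: 81 − 2 = 79.
- Tests and levels only, without antibodies: 21 + 50 = 71.
- Adding one factor-mutation term and three capillary fragility or permeability terms: 81 + 1 + 3 = 85.

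So the count is about 79, with a range of 71 to 85 by rule. A further 35 terms are coagulation disorders or deficiencies with no bleed in the name. Together that is 85 + 35 = 120 clotting-related terms.

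**2. Terms that match scheduled tests**

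SAP Appendix 9 lists only prothrombin time/INR and aPTT under coagulation. The matching Appendix 4 terms are 5 for aPTT, 2 for INR and 4 for prothrombin time or its ratio: 5 + 2 + 4 = 11. The other 79 − 11 = 68 could arise only from testing outside the planned safety panel.

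**3. Which results can become counted events**

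- SAP Section 7.1.1: laboratory AEs are coded in MedDRA together with clinical AEs, so they can match the list.
- Protocol Section 7.1.3: laboratory findings without clinical significance are not AEs. Where a result is part of a syndrome, the syndrome or diagnosis is recorded instead.
- SAP Section 7.1.5.1: the event must start on or after first dose and within 30 days of permanent discontinuation, or lead to discontinuation.
- Study Procedures Table (protocol Appendix 2): coagulation is tested at screening and at the end-of-treatment visit. That visit falls about 30 days after stopping, with a 7-day window either side, so some of its results will fall after the 30-day limit.
- Anticoagulated subjects are foreseen: the exclusion criteria ask for prior discussion of such subjects, and Table 6-3 of the protocol mentions low molecular weight heparin and oral anticoagulants. Unscheduled clotting tests are therefore possible.

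**4. Size per subject**

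Arm B is planned at about 30 subjects: 1/30 = 3.3 points for each subject counted only for such a term. The documents give no frequency. Purely as an assumed range, 0 to 3 subjects would add 0 to 10 points (3/30 = 10.0%).

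**5. Whether the by-term display resolves it**

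A subject with two preferred terms appears in two rows, so the rows cannot be added up to give the number of subjects with a bleed. That number needs its own derivation.

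**The case against.** The strongest reply is that the planned display already separates the terms. A reported aPTT prolongation would stand under its own preferred term, and with about 36 subjects the listing can be read by eye. Choosing a broad search list trades specificity for sensitivity, and nothing in the protocol requires a bleed-only definition. This stands as a reason to expect a small effect and to keep the standard list. It does not supply a count of subjects with a bleed, for the reason in step 5.

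The case for calling immune thrombocytopenic purpura a non-bleed is open to argument. The term names purpura, Appendix 4 treats purpura as bleeding, and the protocol counts petechiae as hemorrhagic. Its absence from the cytopenia list is the firmer part of the point.

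Several stronger readings are tempting, but the documents do not support them:

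- That every prolonged clotting test is counted as bleeding. Only those reported as treatment-emergent AEs are. A result already prolonged before screening that does not worsen is not an AE (Protocol Section 7.1.1).
- That about 79 terms means a large inflation. Most of them correspond to no scheduled test.
- That a headline bleeding rate is distorted, or that bleeding is the main tirabrutinib risk. The SAP names no headline rate, and Protocol Section 1.6 calls clinically significant bleeding unusual.
- That the protocol calls immune thrombocytopenia an expected complication of CLL. The exclusion criterion only bars active autoimmune disease above a stated corticosteroid requirement.
- That Protocol Section 6.6.1 fixes an analysis definition of bleeding. It gives examples.

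**Conclusion.** The point holds as a minor one. As written, the Hemorrhage/Bleeding group mixes bleeds with about 79 test, level and antibody terms (71 to 85 by rule) and with diagnoses that involve no bleed. An event coded to immune thrombocytopenic purpura would be missed by the cytopenia group. Each subject included only through a non-bleeding term adds 3.3 points in Arm B, assuming 30 treated subjects. How many such subjects there will be cannot be derived from the documents. The reporting rules and the sparse schedule suggest few, possibly none. The conclusion rests on the term lists as printed, which the SAP says will be updated to the MedDRA version in use at database finalization.

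**What to change.** Keep the standard Appendix 4 row and add, for summaries A to C, a pre-specified row: haemorrhage, excluding coagulation laboratory, factor-level and antibody terms and non-bleeding diagnoses. List the excluded terms in the appendix and state there how each thrombocytopenic purpura term is handled. Add immune thrombocytopenic purpura to Appendix 6.

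The lists have to be reopened for the MedDRA update in any case, so that is a convenient time. If the SAP is not revised again, its Section 1 provides for documenting the change in the clinical study report.

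The cost is one extra row in three tables, a flag on the term list, and a study-specific subset of the sponsor's standard list. No new data are needed, and keeping the standard row preserves comparability with other uses of that list.

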Appendix 5. Hypersensitivity Medical Search Term

Note: The list presented below is based on a SMQ in MedDRA Version 22.0. The actual list will be up-versioned to the MedDRA version used at the time of database finalization.

MedDRA Preferred Term	PT Code
Acute respiratory failure	10001053
Alveolitis	10001889
Anaphylactic reaction	10002198
Anaphylactic shock	10002199
Anaphylactoid reaction	10002216
Anaphylaxis treatment	10002222
Angioedema	10002424
Application site dermatitis	10003036
Application site rash	10003054
Asthma	10003553
Asthma late onset	10003559
Atopy	10003645
Auricular swelling	10003800
Blepharitis allergic	10005149
Blister	10005191
Blood immunoglobulin A abnormal	10005584
Blood immunoglobulin A increased	10005586
Blood immunoglobulin E abnormal	10005589
Blood immunoglobulin E increased	10005591
Blood immunoglobulin G abnormal	10005594
Blood immunoglobulin G increased	10005596
Blood immunoglobulin M abnormal	10005599
Blood immunoglobulin M increased	10005601
Bromoderma	10006404
Bronchospasm	10006482
Bullous impetigo	10006563
Charcot-Leyden crystals	10008413
Cheilitis	10008417
Choking	10008589
Choking sensation	10008590
Circulatory collapse	10009192
Conjunctival oedema	10010726

MedDRA Preferred Term	PT Code
Conjunctivitis	10010741
Conjunctivitis allergic	10010744
Contrast media reaction	10010836
Corneal oedema	10011033
Cutaneous vasculitis	10011686
Dermatitis	10012431
Dermatitis acneiform	10012432
Dermatitis allergic	10012434
Dermatitis atopic	10012438
Dermatitis bullous	10012441
Dermatitis contact	10012442
Dermatitis exfoliative	10012455
Dermatitis exfoliative generalised	10012456
Dermatitis herpetiformis	10012468
Dermatitis infected	10012470
Drug eruption	10013687
Drug hypersensitivity	10013700
Ear swelling	10014025
Eczema	10014184
Eczema infantile	10014198
Eczema nummular	10014201
Encephalopathy allergic	10014627
Eosinophil count increased	10014945
Eosinophilia	10014950
Eosinophilia myalgia syndrome	10014952
Eosinophilic pneumonia	10014962
Epidermolysis bullosa	10014989
Epiglottic oedema	10015029
Erythema	10015150
Erythema multiforme	10015218
Erythema nodosum	10015226
Eye allergy	10015907

MedDRA Preferred Term	PT Code
Eye swelling	10015967
Eyelid oedema	10015993
Face oedema	10016029
Fixed eruption	10016741
Flushing	10016825
Generalised oedema	10018092
Genital rash	10018175
Giant papillary conjunctivitis	10018258
Gingival swelling	10018291
Henoch-Schonlein purpura	10019617
Hereditary angioedema	10019860
Hypersensitivity	10020751
Hypersensitivity vasculitis	10020764
Idiopathic urticaria	10021247
Immunoglobulins abnormal	10021497
Immunoglobulins increased	10021500
Injection site dermatitis	10022056
Injection site hypersensitivity	10022071
Injection site rash	10022094
Injection site urticaria	10022107
Interstitial lung disease	10022611
Laryngeal oedema	10023845
Laryngospasm	10023891
Laryngotracheal oedema	10023893
Lip oedema	10024558
Lip swelling	10024570
Mouth ulceration	10028034
Mucocutaneous ulceration	10028084
Mucosa vesicle	10028103
Mucosal ulceration	10028124
Multiple allergies	10028164
Nephritis allergic	10029120
Neurodermatitis	10029263
Nikolsky's sign	10029415
Occupational dermatitis	10030012

MedDRA Preferred Term	PT Code
Oculomucocutaneous syndrome	10030081
Oedema mouth	10030110
Oedema mucosal	10030111
Orbital oedema	10031051
Oropharyngeal spasm	10031111
Oropharyngeal swelling	10031118
Panniculitis	10033675
Penile swelling	10034319
Perioral dermatitis	10034541
Periorbital oedema	10034545
Pharyngeal oedema	10034829
Photosensitivity reaction	10034972
Pneumonitis	10035742
Prurigo	10037083
Pruritus	10037087
Pulmonary eosinophilia	10037382
Radioallergosorbent test positive	10037789
Rash	10037844
Rash erythematous	10037855
Rash follicular	10037857
Rash generalised	10037858
Rash macular	10037867
Rash maculo-papular	10037868
Rash morbilliform	10037870
Rash neonatal	10037871
Rash papulosquamous	10037879
Rash pruritic	10037884
Rash pustular	10037888
Rash scarlatiniform	10037890
Rash vesicular	10037898
Reaction to azo-dyes	10037973
Reaction to colouring	10037974
Reaction to food additive	10037977
Red man syndrome	10038192
Respiratory arrest	10038669

MedDRA Preferred Term	PT Code
Respiratory distress	10038687
Respiratory failure	10038695
Rhinitis allergic	10039085
Rhinitis perennial	10039094
Scrotal oedema	10039755
Scrotal swelling	10039759
Serum sickness	10040400
Serum sickness-like reaction	10040402
Shock	10040560
Shock symptom	10040581
Skin erosion	10040840
Skin exfoliation	10040844
Skin necrosis	10040893
Skin reaction	10040914
Skin test positive	10040934
Sneezing	10041232
Solar urticaria	10041307
Solvent sensitivity	10041316
Status asthmaticus	10041961
Stevens-Johnson syndrome	10042033
Stomatitis	10042128
Stridor	10042241
Suffocation feeling	10042444
Swelling face	10042682
Swelling of eyelid	10042690
Swollen tongue	10042727
Throat tightness	10043528
Tongue oedema	10043967
Toxic epidermal necrolysis	10044223
Tracheal obstruction	10044291
Tracheal oedema	10044296
Tracheostomy	10044320
Type I hypersensitivity	10045240
Urticaria	10046735
Urticaria cholinergic	10046740

MedDRA Preferred Term	PT Code
Urticaria contact	10046742
Urticaria papular	10046750
Urticaria physical	10046751
Urticaria pigmentosa	10046752
Urticaria vesiculosa	10046755
Vaginal ulceration	10046943
Vasculitic rash	10047111
Vulval oedema	10047763
Vulval ulceration	10047768
Wheezing	10047924
Acute generalised exanthematous pustulosis	10048799
Urticarial vasculitis	10048820
Seasonal allergy	10048908
Localised oedema	10048961
Allergic sinusitis	10049153
Gingival oedema	10049305
Rash maculovesicular	10050004
Application site eczema	10050099
Application site urticaria	10050104
Vulvovaginal ulceration	10050181
Allergic pharyngitis	10050639
Cytokine storm	10050685
Anti-neutrophil cytoplasmic antibody positive vasculitis	10050894
Complement factor C3 decreased	10050981
Complement factor C4 decreased	10050983
Scleritis allergic	10051126
Allergic cystitis	10051394
Complement factor C1 decreased	10051552
Complement factor C2 decreased	10051555
Generalised erythema	10051576
Infusion related reaction	10051792
Kaposi's varicelliform eruption	10051891
Cytokine release syndrome	10052015
Iodine allergy	10052098

MedDRA Preferred Term	PT Code
Eye oedema	10052139
Eosinophil percentage increased	10052222
Circumoral oedema	10052250
Catheter site rash	10052271
Catheter site urticaria	10052272
Laryngeal dyspnoea	10052390
Urticaria chronic	10052568
Pruritus generalised	10052576
Allergic bronchitis	10052613
Eosinophilic pneumonia acute	10052832
Eosinophilic pneumonia chronic	10052833
Epidermolysis	10053177
Skin swelling	10053262
Injection site photosensitivity reaction	10053396
Type IV hypersensitivity reaction	10053613
Type III immune complex mediated reaction	10053614
Allergic cough	10053779
Streptokinase antibody increased	10053797
Anti-insulin antibody positive	10053814
Anti-insulin antibody increased	10053815
Type II hypersensitivity	10054000
Allergy to fermented products	10054929
Allergy to vaccine	10055048
Eczema weeping	10055182
Allergy test positive	10056352
Encephalitis allergic	10056387
Periorbital swelling	10056647
Mucocutaneous rash	10056671
Bronchial oedema	10056695
Palpable purpura	10056872
Septal panniculitis	10056876
Palatal oedema	10056998
Allergic keratitis	10057380
Scleral oedema	10057431

MedDRA Preferred Term	PT Code
Toxic skin eruption	10057970
Rash rubelliform	10057984
Gastrointestinal oedema	10058061
Eosinophil percentage abnormal	10058133
Dermatitis psoriasiform	10058675
Skin oedema	10058679
Eczema vesicular	10058681
Application site photosensitivity reaction	10058730
Hand dermatitis	10058898
Stoma site rash	10059071
Epidermal necrosis	10059284
Allergic colitis	10059447
Haemorrhagic urticaria	10059499
Laryngeal obstruction	10059639
Infusion site rash	10059830
Alpha tumour necrosis factor increased	10059982
Allergic oedema	10060934
Complement factor decreased	10061048
Eosinophil count abnormal	10061125
Immunology test abnormal	10061214
Mucosal erosion	10061297
Antibody test abnormal	10061425
Antibody test positive	10061427
Arthritis allergic	10061430
Allergic otitis media	10061557
Allergy to chemicals	10061626
Reversible airways obstruction	10062109
Heparin-induced thrombocytopenia	10062506
Necrotising panniculitis	10062579
Dennie-Morgan fold	10062918
Mesenteric panniculitis	10063031
Anaphylactoid shock	10063119
Blood immunoglobulin D increased	10063244
Pruritus allergic	10063438
Allergic respiratory symptom	10063527

MedDRA Preferred Term	PT Code
Allergic respiratory disease	10063532
Application site hypersensitivity	10063683
Implant site rash	10063786
Implant site urticaria	10063787
Vaginal oedema	10063818
Implant site dermatitis	10063855
Implant site hypersensitivity	10063858
Antiallergic therapy	10064059
Eosinophilic oesophagitis	10064212
Lip exfoliation	10064482
Vaginal exfoliation	10064483
Penile exfoliation	10064485
Mucosal exfoliation	10064486
Oral mucosal exfoliation	10064487
Tongue exfoliation	10064488
Corneal exfoliation	10064489
Exfoliative rash	10064579
Immune complex level increased	10064650
Leukotriene increased	10064663
Reaction to preservatives	10064788
Asthmatic crisis	10064823
Laryngitis allergic	10064866
Neutralising antibodies positive	10064980
Non-neutralising antibodies positive	10064982
Perivascular dermatitis	10064986
Infusion site dermatitis	10065458
Infusion site hypersensitivity	10065471
Infusion site photosensitivity reaction	10065486
Infusion site urticaria	10065490
Antiendomysial antibody positive	10065514
Eosinophilic bronchitis	10065563
Visceral oedema	10065768
Eczema vaccinatum	10066042
Bronchial hyperreactivity	10066091
Allergic transfusion reaction	10066173

MedDRA Preferred Term	PT Code
Injection site eczema	10066221
Penile oedema	10066774
Injection site recall reaction	10066797
Gleich's syndrome	10066837
Contrast media allergy	10066973
Anaphylactic transfusion reaction	10067113
Haemolytic transfusion reaction	10067122
Immediate post-injection reaction	10067142
Oculorespiratory syndrome	10067317
Contact stomatitis	10067510
Genital swelling	10067639
Upper airway obstruction	10067775
HLA marker study positive	10067937
Oropharyngeal blistering	10067950
Interstitial granulomatous dermatitis	10067972
Mucosal necrosis	10067993
Injection site vasculitis	10067995
Anti-insulin receptor antibody positive	10068225
Anti-insulin receptor antibody increased	10068226
Oral allergy syndrome	10068355
Capillaritis	10068406
Mechanical urticaria	10068773
Palisaded neutrophilic granulomatous dermatitis	10068809
Vaccination site hypersensitivity	10068880
Kounis syndrome	10069167
Henoch-Schonlein purpura nephritis	10069440
Vaccination site dermatitis	10069477
Vaccination site rash	10069482
Vaccination site exfoliation	10069489
Vaccination site urticaria	10069622
Vaccination site vesicles	10069623
Administration related reaction	10069773
Limbal swelling	10070492
Distributive shock	10070559

MedDRA Preferred Term	PT Code
Immune tolerance induction	10070581
Respiratory tract oedema	10070774
Reactive airways dysfunction syndrome	10070832
Occupational asthma	10070836
Injection related reaction	10071152
Administration site rash	10071156
Allergic hepatitis	10071198
Vulvovaginal swelling	10071211
Chronic hyperplastic eosinophilic sinusitis	10071380
Chronic eosinophilic rhinosinusitis	10071399
Vulvovaginal rash	10071588
Device allergy	10072867
Incision site dermatitis	10073168
Blister rupture	10073385
Incision site rash	10073411
Implant site photosensitivity	10073415
Drug reaction with eosinophilia and systemic symptoms	10073508
Instillation site hypersensitivity	10073612
Instillation site rash	10073622
Instillation site urticaria	10073627
Catheter site dermatitis	10073992
Catheter site eczema	10073995
Catheter site hypersensitivity	10073998
Catheter site vasculitis	10074014
Allergy to immunoglobulin therapy	10074079
Pathergy reaction	10074332
Drug provocation test	10074350
Palatal swelling	10074403
Stoma site hypersensitivity	10074509
Immune thrombocytopenic purpura	10074667
Noninfective conjunctivitis	10074701
Infusion site eczema	10074850
Infusion site vasculitis	10074851
Caffeine allergy	10074895

MedDRA Preferred Term	PT Code
Transplantation associated food allergy	10075008
Allergic otitis externa	10075072
Aspirin-exacerbated respiratory disease	10075084
Administration site dermatitis	10075096
Administration site eczema	10075099
Administration site hypersensitivity	10075102
Administration site urticaria	10075109
Allergic eosinophilia	10075185
Mouth swelling	10075203
Airway remodelling	10075289
Allergic gastroenteritis	10075308
Perineal rash	10075364
Allergy alert test positive	10075479
Medical device site dermatitis	10075572
Medical device site eczema	10075575
Medical device site hypersensitivity	10075579
Medical device site rash	10075585
Medical device site urticaria	10075588
Nodular rash	10075807
Administration site photosensitivity reaction	10075961
Administration site recall reaction	10075964
Administration site vasculitis	10075969
Application site recall reaction	10076024
Application site vasculitis	10076027
Infusion site recall reaction	10076085
Medical device site photosensitivity reaction	10076137
Medical device site recall reaction	10076140
Vaccination site eczema	10076161
Vaccination site photosensitivity reaction	10076186
Vaccination site recall reaction	10076188
Vaccination site vasculitis	10076191
Intestinal angioedema	10076229
Documented hypersensitivity to administered product	10076470

MedDRA Preferred Term	PT Code
Mast cell degranulation present	10076606
Dialysis membrane reaction	10076665
Asthma-chronic obstructive pulmonary disease overlap syndrome	10077005
Vessel puncture site rash	10077117
Allergy to surgical sutures	10077279
Immune-mediated adverse reaction	10077665
Vessel puncture site vesicles	10077813
Eosinophilic granulomatosis with polyangiitis	10078117
Symmetrical drug-related intertriginous and flexural exanthema	10078325
Nasal crease	10078581
Oropharyngeal oedema	10078783
Allergic reaction to excipient	10078853
Allergic stomatitis	10079554
Therapeutic product cross-reactivity	10079645
Reaction to excipient	10079925
Vulvovaginitis allergic	10080783
Procedural shock	10080894
Hereditary angioedema with C1 esterase inhibitor deficiency	10080955
Vernal keratoconjunctivitis	10081000
Hypersensitivity myocarditis	10081004
Acquired C1 inhibitor deficiency	10081035
Scrotal exfoliation	10081178
Childhood asthma	10081274
Atopic cough	10081492
Circumoral swelling	10081703
Hypersensitivity pneumonitis	10081988
Human anti-hamster antibody increased	10082107
Human anti-hamster antibody positive	10082109
Pharyngeal swelling	10082270
Urticarial dermatitis	10082290
Immune-mediated pneumonitis	10082452

